10.8.3 Vital Signs

Vital signs, including HR (based on measurement of pulse), and their change from baseline will be summarized by actual treatment group and scheduled assessment.

10.8.4 Electrocardiogram (ECG)

For post-baseline assessments where ECG is performed in triplicate, the average of the 3 (or all available) readings will be used for analysis. Observations with the following diagnosis or findings will be excluded from analysis: artificial pacemaker, atrial fibrillation, atrial flutter, left bundle branch block, and right bundle branch block.

PR, RR, QRS, QT, QTcB and QTcF intervals and their change from baseline will be summarized by actual treatment group and scheduled assessment.

Subjects will be categorized into the following groups per their maximum change from baseline in QTcB and QTcF. Unscheduled assessments will be included in the determination of the maximum change. The number and percentage of subjects in each group will be summarized.

- \leq 30 msec
- $>$ 30 – 60 msec
- $>$ 60 msec

Subjects will also be categorized into the following groups per their maximum post-baseline QTcB and QTcF. Unscheduled assessments will be included in the determination of the maximum post baseline value. The number and percentage of subjects in each group will be summarized.

- \leq 450 msec
- $>$ 450 – 480 msec
- $>$ 480 – 500 msec
- $>$ 500 msec

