Japanese male and female subjects ≥ 20 and ≤ 85 years of age with chronic stable HF with reduced ejection fraction; treated with optimal pharmacological therapy, including a beta blocker and either an angiotensin-converting enzyme (ACE) inhibitor or an angiotensin receptor blocker (ARB) that is expected to remain stable over the period of participation in the study, unless not tolerated; and left ventricular ejection fraction (LVEF) must be $\leq 40\%$ as determined by central reading of the screening echocardiogram. Enrollment of subjects with atrial fibrillation/flutter is limited to up to approximately 20% of planned enrollment in the study. Randomization will be stratified by presence or absence of atrial fibrillation/flutter at the time of screening via interactive voice response system/interactive Web response system (IVRS/IWRS).

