10.5.4.4 Electrocardiogram

Summaries over time and/or changes from baseline over time will be provided for all ECG parameters.

Subjects' maximum change from baseline in QT Fridericia corrected will be categorized and the number and percentage of subjects in each group will be summarized.

Subjects' maximum post baseline values will also be categorized and the number and percentage of subjects in each group will be summarized.

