4.1.3 Safety Endpoints

Safety endpoints are as follows:

- Subject incidence of adverse events (AEs)
- Changes from baseline in laboratory values and vital signs
- Changes from baseline in ECG

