6.2 Demographics and Baseline Related Definitions

Age

Age will be calculated as the subject's age in years at enrollment as recorded on the eCRF.

Baseline ECG

For ECG, the baseline value is defined as the mean over all non-missing triplicate averages of 3 (or all available) readings from each set of triplicate taken prior to or on Study Day 1.

Other Baseline Values

For all other variables, the baseline value is defined as the last non-missing value collected prior to or on Study Day 1.

Change from Baseline

The arithmetic difference between a post-baseline value and baseline for a given time point:

Change from baseline = (post-baseline value – baseline value).

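### SAP 10.8.4 removes bundle-branch-block, paced and AF/flutter tracings from every ECG interval summary, QRS included, and reports no count of what was removed

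*SAP*

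**What the plan says.** ECG change is a named safety endpoint (SAP 4.1.3: "Changes from baseline in ECG"), and safety is one of the two primary objectives.

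SAP 10.8.4 first says that post-baseline triplicates are averaged. It then says "Observations with the following diagnosis or findings will be excluded from analysis", and the list is "artificial pacemaker, atrial fibrillation, atrial flutter, left bundle branch block, and right bundle branch block". Two sets of outputs follow under that rule:

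- interval summaries: "PR, RR, QRS, QT, QTcB and QTcF intervals and their change from baseline will be summarized by actual treatment group and scheduled assessment"
- worst-case categories: "Subjects will be categorized into the following groups per their maximum change from baseline in QTcB and QTcF", with a parallel set for the maximum post-baseline value.

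No wording limits the rule to QT/QTc, or to subjects who already had the finding at entry. The baseline definition in SAP 6.2 ("the baseline value is defined as the mean over all non-missing triplicate averages of 3 (or all available) readings") mentions no exclusion.

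Protocol 10.5.4.4 describes the ECG analysis in general terms: "Summaries over time and/or changes from baseline over time will be provided for all ECG parameters". It has no rhythm or conduction exclusion.

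**The concern.** Leaving such tracings out is easy to defend for some intervals. PR is undefined in AF, and QTc is hard to read when the QRS is wide or paced. The SAP, however, applies one list to all six intervals and works at the level of the observation.

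For QRS this makes missingness depend on the value being measured. A subject whose QRS widens on treatment until the reader records bundle branch block loses that tracing and keeps the narrower ones. The group mean then describes only tracings that did not reach block. The same subject's worst-case QTc category is set by the tracings that remain.

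SAP 10.8 plans no table of rhythm or conduction shifts, no count of excluded tracings by group, and no ECG sensitivity analysis. A reader of the study report could not tell whether one group lost more tracings than another. Troponin, by contrast, gets a baseline-to-worst table in SAP 10.8.2.

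**Working it through.** **The plan's own figure.** The only precision figure in the plan is the PK half-width in SAP 3.2. It reproduces as 1.96 × SD/√19: 17.99 for SD 40 and 40.47 for SD 90, against 18.0 and 40.5 in the table. It does not bear on ECG. The plan gives no QRS variance, no expected rate of block or pacing, and no ECG precision target.

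**Where each finding can still be seen.** Set against every ECG and arrhythmia analysis in the two documents:

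| New finding on treatment | ECG interval tables | Other planned route |
|---|---|---|
| AF/flutter | removed | exploratory endpoint, incidence by group (SAP 4.1.4, 10.7); adverse events |
| Heart-rate change during AF | RR removed | HR from pulse (SAP 10.8.3); HR in a repeated-measures model (SAP 10.7), neither with a rhythm exclusion |
| LBBB or RBBB | removed | adverse events only |
| Pacing | removed | adverse events only |
| PR prolongation, or QRS widening not read as block | kept | not needed |

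The adverse event route is incomplete for block. Protocol 7.2.11 has tracings read centrally but does not require the investigator's reading to be reconciled with the central one. A block recorded only by the central reader need not become an adverse event.

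**Illustration 1: a smooth shift (all inputs assumed).** Baseline QRS is normal with mean 100 ms and SD 12, restricted to below 120 ms. The individual change has SD 7 and mean 0 on placebo or +8 ms on active. A post-baseline value of 120 ms or more is labelled block and dropped. Integrating over the baseline distribution:

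- placebo: 4.3% of readings dropped, mean change in those kept −0.44 ms
- active: 15.6% dropped, mean change in those kept +6.84 ms
- difference reported: 6.84 − (−0.44) = 7.28 ms, against a true 8 ms, so about 0.7 ms is lost.

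For scale, the 95% half-width for a two-group difference with change SD 7 and 20 per group is 2.024 × 7 × √(2/20) = 4.5 ms.

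**Illustration 2: a concentrated effect (all inputs assumed).** In an arm of 20, k subjects develop block with QRS +40 ms and the others do not change. The true mean change is 40k/20, which is 2, 4, 6 or 8 ms for k = 1 to 4. Under the rule the table shows 0 ms each time. This is a deliberately extreme construction. It shows only that the answer depends on inputs the plan does not supply.

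**Tracings lost to pre-existing AF.** Per the protocol synopsis, "Enrollment of subjects with atrial fibrillation/flutter is limited to up to approximately 20% of planned enrollment in the study". The ceiling is 0.20 × 80 = 16 subjects, or about 4 of 20 per arm. If the cap is filled and AF persists on every tracing, 16 per arm remain. A t-based interval then widens by (2.131/√16)/(2.093/√20) = 1.14, about 14%. That is a loss of precision and not a bias.

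**The case against.** **New AF is not lost to the trial.** A reader might infer that new on-treatment AF disappears from the safety evaluation. The documents do not support that: it is a named exploratory endpoint with incidence by group, treated supraventricular and ventricular tachycardias are counted separately, and adverse events are tabulated. AF leaves only the interval averages. This objection stands.

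**RR is largely covered.** RR is the reciprocal of heart rate, which is analysed from pulse and in a model. Nothing in the documents shows that RR summaries are biased toward no effect. This stands too; keeping RR is a matter of completeness.

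**The AF stratum is not silent.** It might be inferred that this stratum contributes no ECG data. The stratum is defined at screening, whereas the rule removes observations, so any tracing in another rhythm stays in. The 16 is also a ceiling, not an expected count.

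**The bias may be small.** Under Illustration 1 it is about one-seventh of the sampling half-width, in a descriptive trial with no hypothesis test. Every input is assumed, and the SAP does not equate 120 ms with a block label. This is fair as regards the mean. It does not answer the unequal, unreported loss of readings.

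**Departure from the protocol.** One could call the rule an undeclared change, because SAP Section 11 does not list it. That is arguable: Protocol 10.5.4.4 is general, supplying analysis detail is the SAP's stated purpose, and the listed intervals are still summarised. The point does not rest on it.

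**Conclusion.** The point stands in a limited form. SAP 10.8.4 applies one exclusion list to all intervals, makes no distinction between baseline and new findings, and for QRS selects on the outcome. What goes unseen is new bundle branch block and new pacing on the centrally read ECG, for which adverse event reporting is the only other route and an incomplete one.

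The size of any bias cannot be derived from the documents. Under the smooth-shift assumptions it is about 0.7 ms on a true 8 ms effect. The clearer signal there is differential loss, 16% of active against 4% of placebo readings, which no planned table would reveal. It is also unclear whether the rule reaches baseline tracings: the sentence follows one on post-baseline triplicates, and SAP 6.2 is silent.

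A reader might conclude that the whole exclusion should be dropped. It should not. PR in AF/flutter is undefined, and QTc in block or pacing is confounded by QRS width. The exclusion should be narrowed by interval and made visible.

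**What to change.** In SAP 10.8.4, replace the single list with a rule by interval, applied alike at baseline and post-baseline:

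- **PR:** exclude tracings in AF/flutter or pacing.
- **QT, QTcB, QTcF:** exclude tracings with pacing or bundle branch block, as now, and add a sensitivity analysis that includes tracings with new bundle branch block. State explicitly how QT/QTc in AF/flutter is handled, since the present rule excludes it.
- **RR and QRS:** keep all unpaced tracings, including those with new AF or new bundle branch block.

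Add one table by treatment group showing subjects with new post-baseline LBBB, RBBB, pacing or AF/flutter on the centrally read ECG, and the number of tracings excluded at each visit. The AF/flutter row partly overlaps the exploratory endpoint, but it comes from a single source, the central reading.

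State in SAP 6.2 whether the rule applies to the baseline ECG.

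The cost is SAP wording and one or two tables. The protocol already collects and centrally reads the tracings, so no new data are needed. The downside is slightly noisier QRS and RR summaries.

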10.8.5 Exposure to Investigational Product

Descriptive statistics will be produced to describe the exposure to investigational product by treatment group. Indicators of extent of IP exposure include total IP administration duration and dosing compliance.

Exposure definitions are provided in [Section 6.4](#).

10.8.6 Exposure to Concomitant Medication

Concomitant medications will be coded by the World Health Organization Drug (WHO DRUG) dictionary. The number and proportion of subjects receiving oral medications of interest will be summarized by medication category, preferred term and regimen dose, unit and frequency at baseline and EOS for each treatment group.

11. Changes From Protocol-specified Analyses

During the initial development of this document, it was realized that there are protocol-specified analyses that cannot be implemented/Performed and the protocol is not required to be amended. HF treatment at baseline will not be included as a baseline covariate. HF treatment, including BB, ACEi or ARB, is one of the expansion phase inclusion criteria and therefore the study is not expected to support subgroup analysis of no HF treatment at baseline. These changes will also be documented in the Clinical Study Report.

The definition of the PKAS was clarified to require one evaluable PK concentration rather than PK parameter as stated in the protocol.

12. Literature Citations / References

13. Data Not Covered by This Plan

This SAP does not address the analysis for the secondary objective

- to explore the potential relationship between omecamtiv mecarbil exposure and changes from baseline in SET

14. Appendices

Appendix A. Analytical Study Week Assignments

Selected endpoints will be summarized by scheduled study visits in descriptive analyses. Since the actual visits may not exactly coincide with their scheduled visit day, the actual visit day is mapped to the study visit by non-overlapping consecutive intervals covering the entire time continuum. The mapping intervals for all distinct schedules are summarized in the following table, for non-PK endpoints:

Scheduled visit	Actual Visit Day (Study Day)							
	VS*, CC, ECG	WT, CH, HE	PE	NT	ECHO	UR	DG	NYHA
BL/Day 1	≤ 1	≤ 1	≤ 1	≤ 1	≤ 1	≤ 1	≤ 1	≤ 1
Day 15 (Week 2)	> 1 – ≤ 21	> 1 – ≤ 35						> 1
Day 28 (Week 4)	> 21 – ≤ 42			> 1 – ≤ 42				
Day 56 (Week 8)	> 42 – ≤ 70	> 35 – ≤ 70		> 42 – ≤ 84	> 1 – ≤ 84	> 1 – ≤ 98		
Day 84 (Week 12)	> 70 – ≤ 98	> 70 – ≤ 98						
Day 112 (Week 16)	> 98 – ≤ 126	> 98 – ≤ 126		> 84	> 84			
Day 140 (Week 20)	> 126	> 126	> 1			> 98		

VS: vital signs; WT: body weight; CC: cardiac troponin and CK-MB; PE: physical examination; NT: NT-proBNP; ECHO: electrocardiography; CH: chemistry; HE: hematology; UR: urinalysis; DG: Digoxin.
*Vital signs on week 8 and 16 are to be measured multiple times for E-R analysis purpose, and the value before morning dose will be used for non-PKPD analysis.

Handling multiple records assigned to an analytical study day/week:

If there is more than one record in a study week interval, the analytical record for that specific study week will be defined as the record closest to the scheduled study day of that specific study week ($7 \times$ study week + 1). If two records are equidistant from the scheduled day, then the earlier record will be chosen. If there are multiple records on the same day, the last record will be used.

Exceptions to these rules are:

- vital signs, the latest one prior to first IP administration on that day will be used in the non-PKPD analysis;
- cardiac troponin, CK-MB, and creatine kinase, where the worst non-missing value within the interval will be used in the analysis.

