2.2.2.1 Studies in Healthy Volunteers

CY 1111, a first-in-human clinical study with omecamtiv mecarbil, was a randomized, double-blind, placebo-controlled, 4-period crossover, dose escalation study designed to evaluate the safety, tolerability, and PK/PD profile of omecamtiv mecarbil administered IV to healthy male volunteers ([Teerlink et al, 2011](#)). This study included a total of 33 subjects who received infusions of omecamtiv mecarbil at doses ranging from 0.005 mg/kg/hr to 1.0 mg/kg/hr for up to 6 hours. The exposures of omecamtiv mecarbil, as measured by area under the curve (AUC) and maximum observed concentration (C_{max}), were approximately dose proportional, with an AUC of 159 (57 standard deviation) ng•hr/mL for treatment administered at an infusion rate of 0.005 mg/hr/kg and 30400 ng•hr/mL when administered at a rate of 1 mg/hr/kg; corresponding C_{max} values for those administration rates were 8.70 (2.20) ng/mL and 1340 ng/mL. The mean clearance ranged from 125 to 207 mL/hr/kg and the mean half life ranged from 17.1 to 23.2 hours and increased slightly with increasing doses. The mean steady state distribution volume was dose independent and ranged from 3.6 to 5.2 L/kg. At the dose of 0.5 mg/kg/hr over 6 hours, the mean (standard deviation [SD]) C_{max} was 905 (183) ng/mL. Across the dosing levels evaluated in CY 1111, omecamtiv mecarbil infusions demonstrated generally linear PK with dose-proportional increases in C_{max} . Concentration-dependent PD effects on cardiac function as measured by echocardiography were observed. These PD effects included statistically significant placebo corrected increases from baseline in SET, Doppler-derived stroke volume, left ventricular ejection fraction (LVEF), and fractional shortening.

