6.2.1.1 Dosage, Administration, and Schedule

Eligible outpatient subjects will be randomized and will initiate administration of IP (omeamtiv mecarbil or placebo). Day 1 is defined as the calendar day when treatment with IP is initiated. The first administration of IP should be on the day of randomization but not later than 5 calendar days after randomization. The time when ingestion of the first dose of IP is completed is defined as Time = 0 hours. Baseline procedures must be completed before initiation of IP and can be performed on the same day.

IP will be administered orally BID in the morning and evening by the subjects and can be taken under fasted or fed conditions. IP will be swallowed whole (not chewed) and taken with water as instructed in the IPIM. Administration of each morning and evening dose is to be taken at approximately the same time of day (12 ± 3 hours from the most recent previous dose). If IP cannot be taken or has not been taken within this window, the dose should be recorded as missed and the next dose should be taken at the regular time.

Administration of IP will start with the morning dose on day 1 and will end with the morning dose on the day of the subject's week 16 visit. The quantity, date and time, lot number, and bottle number of investigational product is to be recorded on each subject's eCRF.

6.2.1.2 Rules for Withholding Investigational Product due to Myocardial Ischemia or Infarction, Abnormal Blood Pressure or Heart Rate

Omecamtiv mecarbil may result in signs and symptoms of myocardial ischemia or infarction, as described in Section 7.1 of the Investigator's Brochure (eg, increases in HR, dizziness, dyspnea, hypotension, chest discomfort or pain, ST-segment depression on ECG, and/or elevations in troponin I or T). If a subject reports clinical signs or symptoms suggestive of myocardial ischemia or infarction, and/or experiences changes in BP or HR, withholding of IP should be considered. No antidote to omecamtiv mecarbil exists. Standard medical therapies should be used in the presence of signs or symptoms of myocardial ischemia.

The following are mandatory rules for withholding IP:

- The subject experiences clinical signs or symptoms, including ECG changes, consistent with myocardial ischemia or infarction as determined by the investigator
- The subject experiences a symptomatic decrease in systolic BP on 2 successive measurements

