^j Vital signs and PK samples at predose, at 2 hours \pm 30 minutes; 4 hours \pm 30 minutes; 6 hours \pm 30 minutes; 8 hours \pm 30 minutes after IP administration in the morning (0 h = start of IP); echocardiogram performed as close as possible after the collection of PK sample at 2 hours \pm 30 minutes following IP administration.

^k Vital signs and PK samples at predose and at 2 hours \pm 30 mins following IP administration. Echocardiogram should be performed as close as possible after the collection of PK sample at 2 hours \pm 30 minutes following IP administration.

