up-titrated at week 8 based on the steady state C_{predose} result from week 2, if available. Subjects will be up-titrated to 37.5 mg BID or 50 mg BID at the week 4 or week 8 visits in the titration groups only if the week 2 C_{predose} is < 200 ng/mL. Subjects with a week 2 $C_{\text{predose}} \geq 200$ ng/mL (or not available at week 8) will continue at 25 mg BID for the remainder of the study. Subjects randomized to placebo or to 25 mg BID will receive the assigned IP throughout the study. IP compliance will also be monitored. PK analysis and dose assignment will be blinded to the study team. To maintain blinding, all subjects will receive new IP supply at the week 4 and week 8 visits. The study includes transthoracic echocardiographic assessments (screening, week 8, and week 16). Enrollment of subjects with atrial fibrillation/flutter at the time of screening will be limited to approximately 20% of planned enrollment. Randomization will be stratified by presence or absence of atrial fibrillation/flutter via the interactive voice response system/interactive Web response system (IVRS/IWRS).

An independent DMC will perform regular formal unblinded review of the accumulating study data. An independent CEC will adjudicate deaths, all hospitalizations, and selected nonfatal cardiovascular (CV) events (including possible MI or ischemia). The end of study (EOS) visit will be performed 4 weeks after the last dose of IP (Week 20 +3 days).

Vital signs, physical examinations, ECGs, Adverse Event/Serious Adverse Event assessments, clinical laboratory evaluations (see Table 3 in protocol), and collection of concomitant medications will be performed at screening and at specified times per the Schedule of Assessments (see Table 2 in protocol). The overall study design is described by a study schema at the end of the protocol synopsis section. Detailed study procedures are provided in Protocol Section 7. The study endpoints are defined in [Section 4.1](#).

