6.4 Other Study Related Definitions

Analytical Study Week Assignments

Analytical windows will be used to assign parameters to study days/weeks. The algorithm is provided in [Appendix A](#).

Actual Treatment Group

A subject's actual treatment group is the randomized treatment group, unless the subject receives the same treatment throughout the study that is different to the randomized treatment group assignment, in which case the actual treatment group is the treatment received. For subjects randomized to omecamtiv mecarbil 37.5 mg BID and 50 mg BID, the actual treatment groups: 25 mg (Not up-titrated to 37.5 mg), 25 mg (Up-titrated to 37.5 mg) and 25 mg (Not up-titrated to 50 mg), 25 mg (Up-titrated to 50 mg) respectively, includes only those subjects who have a minimum IP exposure period of 25 days. Titration status groups may be used in select outputs and these four actual treatment groups should only be compared to each other. The omecamtiv mecarbil

Overall 37.5 mg BID, and Overall 50 mg BID actual treatment groups include all the subjects included in the omecamtiv mecarbil 37.5 mg BID, and 50 mg BID randomized treatment groups respectively.

Investigational Product (IP)

IP includes Omecamtiv Mecarbil 25 mg BID, 37.5 mg BID, and 50 mg BID and Placebo BID.

IP Dose Administered (mg)

From IP administration eCRF, number of tablets administered from each box is # dispensed - # lost or missing - # returned. If any of these numbers is missing, the sum of tablets reported on the IP administration eCRF for the same box will be used. IP dose administered is the sum of all the tablets' dose from all boxes dispensed.

IP Compliance (%)

Total IP dose administered divided by the total planned dose (223 tablets), multiplied by 100.

IP Exposure Period in Days

((Last IP administration date in the IP administration form – date of Study Day 1) + 1.

IP Exposure Period in Weeks

((Last IP administration date in the IP administration form – date of Study Day 1) + 1) / 7.

Study Exposure Period in Days

For each randomized subject, Study Exposure Period = (EOS Date – Randomization Date) + 1.

Study Exposure Period in Weeks

For each randomized subject, Study Exposure Period = ((EOS Date – Randomization Date) + 1) / 7.

Treatment-Emergent Adverse Event (TEAE)

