10.6 Analyses of Secondary Endpoint

Echocardiographic parameters and their change from baseline will be summarized by randomized treatment group and scheduled assessment.

Mean differences between treatment groups in SET change from baseline at week 16 will be estimated via repeated-measures model including all observed values, with difference estimates and their 95% confidence intervals presented. The model will include IVRS stratification factor, baseline, treatment group, visit and the interaction of treatment group and visit. Individual subgroup analyses by the IVRS stratification factor and selected baseline covariates as listed in [Section 4.2](#) will be provided. Baseline covariates may also be included in the model one at a time in their original form.

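### SAP Appendix A puts no on-treatment or post-titration limit on the week-8 and week-16 echo windows, which matters only if a scheduled echo is missing and another echo stands in for it

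*SAP*

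**What the plan says.** The sole secondary endpoint is change from baseline in SET at week 16 (Protocol 10.1.1.2, SAP 4.1.2). SAP 6.4 states: "Analytical windows will be used to assign parameters to study days/weeks". Appendix A then says that "the actual visit day is mapped to the study visit by non-overlapping consecutive intervals covering the entire time continuum".

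In the Appendix A table:

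- ECHO week 8 is Study Days 2 to 84, and week 16 is every day after Day 84.
- NT-proBNP week 8 is Days 43 to 84, and week 16 is every day after Day 84.
- Vital signs, ECG, troponin/CK-MB, weight, chemistry and hematology have a week-16 window of Days 99 to 126. It closes there because these columns also have a week-20 row.

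If an interval holds several records, "the analytical record for that specific study week will be defined as the record closest to the scheduled study day". SET differences "will be estimated via repeated-measures model including all observed values" (SAP 10.6). SAP 7.4 and 10.1 add a sensitivity analysis in subjects who completed IP.

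The protocol intends a timed, on-drug measurement. On the week-16 echo, the Schedule of Assessments says: "Echocardiogram should be performed as close as possible after the collection of PK sample at 2 hours". Dosing "will end with the morning dose on the day of the subject's week 16 visit" (Protocol 6.2.1.1).

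**The concern.** SET is a pharmacodynamic measure that should be read on drug and, at week 8, normally after the week-4 titration step. Because the windows cover all time, Appendix A rejects no echo for its date, and nothing else in the SAP asks whether the subject was still taking IP.

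If a subject has no usable scheduled echo, a lone record from before titration would enter as week 8, and a lone record from after dosing ended would enter as week 16. The first would blur the week-8 comparison between doses, since all active arms take 25 mg BID until the week-4 visit. The second would pull an active arm's week-16 difference from placebo toward zero. For NT-proBNP only the open week-16 window is at issue.

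**Working it through.** **1. Reproduce the table.** Each cut-point is the midpoint of adjacent scheduled days, rounded down:

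- ECHO: (56 + 112)/2 = 84
- NT-proBNP: (28 + 56)/2 = 42 and (56 + 112)/2 = 84
- Urinalysis: (56 + 140)/2 = 98
- Vital signs/ECG: 21.5, 42, 70, 98, 126

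All agree with Appendix A, so the limits are the stated rule and not an extraction fault. The footnote expands ECHO as electrocardiography, but ECG has its own column and only the echocardiogram follows the Day 56/Day 112 schedule.

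**2. Apply the rule.**

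| Echo on Study Day | Filed as | Status |
|---|---|---|
| 10, 20 or 27 | week 8 | before the earliest week-4 titration (Day 28) |
| 56 | week 8 | scheduled |
| 112 | week 16 | scheduled, day of last dose |
| 130 or 140 | week 16 | after dosing, if the last dose was at an on-time week-16 visit (Days 109 to 115) |

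The week-8 window is 84 − 1 = 83 days wide, of which Days 2 to 27 (26 days) precede any titration. The protocol's visit window is 7 days (Day 56 ± 3). A vital-signs record on Day 130 would be filed as week 20.

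**3. Apply the nearest-record rule.** The target is 7 × week + 1, that is Day 57 or Day 113. A scheduled Day 56 echo is 1 day away and a Day 10 echo is 47. A scheduled Day 112 echo is 1 day away and a Day 140 echo is 27. The scheduled record wins whenever the competitor is distant. There is one narrow exception. If the week-16 visit falls on Day 109 (4 days away), a repeat echo on Day 113 (0 days away) would be preferred. The last-dose flag proposed below catches that case.

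**4. Drug remaining after the last dose.** The input is Protocol 2.2.2.1: "the mean half life ranged from 17.1 to 23.2 hours". Fraction remaining = 0.5^(hours/half-life), assuming first-order elimination.

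| Days off drug | Hours | Half-lives (at 23.2 h to 17.1 h) | Remaining |
|---|---|---|---|
| 1 | 24 | 1.0 to 1.4 | 49% to 38% |
| 5 | 120 | 5.2 to 7.0 | 2.8% to 0.8% |
| 14 | 336 | 14 to 20 | below 0.01% |
| 28 | 672 | 29 to 39 | effectively 0 |

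These half-lives come from intravenous dosing in healthy male volunteers. If the longer one were doubled to 46.4 h, 28 days would still be 672/46.4 = 14 half-lives.

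**5. Dilution.** Suppose k of an arm's n week-16 values are fully off drug and the rest carry a mean effect D. The arm's mean effect is then D(n − k)/n, a loss of k/n. For n = 20, k = 0 gives 0% and k = 1 gives 1/20 = 5%. The documents give no value for k.

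**The case against.** The strongest reply is that the study does not plan such records. Echoes are scheduled only at screening, week 8 and week 16. The week-20 visit includes neither an echo nor NT-proBNP, and the early-discontinuation visit uses the week-20 assessments (Protocol 7.1 and 7.5). Extra records are handled by the nearest-record rule. A misfiled week-8 value mainly affects the week-8 estimate, because the model has a treatment-by-visit term. The study is descriptive, with no hypothesis test. All of this stands and limits the point to a minor improvement.

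A reader might infer three stronger things that the documents do not support:

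- **That missed week-16 echoes will be made up at week 20.** Nothing provides for this.
- **That any late week-16 echo is off drug.** Dosing ends on the day of the week-16 visit, so if the whole visit slips, the last dose slips with it.
- **That the week-16 effect is diluted by 5% to 15%.** That would require 1 to 3 off-drug values per arm of 20. No frequency is given, and the range starts at 0%.

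It can also be said that the completer analysis already covers off-drug values. It does so in part. It removes a subject who stopped IP, stayed in the study (Protocol 8.1 allows this) and had an on-time echo, a case no window can catch. It keeps a completer whose only week-16 echo was taken after the last dose.

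**Conclusion.** The concern holds in a limited form. The open windows are a stated rule, and under it a lone pre-titration or post-dosing echo would be analysed as week 8 or week 16. With the narrow exception shown in the working, this needs two things together: no usable scheduled echo, and an unscheduled or substitute one in the data.

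The number of such records is unknown and may be zero, so the expected effect cannot be stated. The conditional effect is about 1/n of an arm's mean SET effect per fully off-drug week-16 value, or about 5% if all 20 subjects contribute. This assumes total loss of effect off drug, which is reasonable at two weeks or more but not at one day.

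The windows cannot resolve every mismatch. A subject titrated at the week-8 visit because the week-2 concentration was late may have a week-8 echo at the starting dose under any limits.

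**What to change.** Make these changes before unblinding:

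1. In Appendix A, set ECHO week 8 to > 42 to ≤ 84, and ECHO and NT-proBNP week 16 to > 84 to ≤ 126. Days 42 and 126 are already limits in that table, and Day 42 lies after the week-4 visit window (Days 28 to 31).
2. Amend the sentence on covering all time, and state that ECHO and NT-proBNP records outside these limits are left unassigned and listed.
3. Flag any week-16 echo taken more than 1 day after the last IP, and repeat the SET model without flagged records, reported beside the completer analysis.

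Item 3 does most of the work. With a last dose on Day 112, the Day 126 limit still admits an echo 14 days later, or 14 to 20 half-lives. The flag also identifies subjects who stopped IP early but had an on-time echo. Flagged records within the window stay in the main model.

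The cost is three table cells, a short text change, one derived flag and one extra model run. The drawback is that a few off-window values may leave the by-visit model; those subjects would have no value at that visit, since the SAP does not impute.
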